4.4.2.3 Progression-Free Survival by Investigator Using RECIST v1.1

PFS, as determined by the investigator according to RECIST v1.1, will be analyzed using the same methods as described for PFS by IRC in Section [4.4.1](#).

4.4.2.4 Disease Control Rate by IRC and Investigator Using RECIST v1.1

DCR is defined as the proportion of ITT patients with measurable disease at baseline with a complete response, a partial response, or stable disease at 16 weeks after the baseline tumor assessment, as determined by the IRC or investigator according to RECIST v1.1. A 95% Clopper-Pearson CI will be calculated for the DCR for each treatment arm.

4.4.2.5 Duration of Response by IRC and Investigator Using RECIST v1.1

For patients who achieve an objective response, DOR is defined as the time from the first occurrence of a documented objective response to disease progression, as determined by the IRC or investigator according to RECIST v1.1, or death from any cause, whichever occurs first. The censoring method for DOR will be the same as that for PFS. The Kaplan-Meier approach will be used to estimate median DOR. The 95% CI of the median DOR will be estimated using the Brookmeyer and Crowley method ([Brookmeyer and Crowley 1982](#)). Comparisons of DOR between treatment arms will be for descriptive purposes only.

4.4.2.6 Patient-Reported Outcomes

The data from the PRO-evaluable population, which includes all randomized patients who have a baseline and at least 1 post-baseline assessment, will be used to assess change from baseline in global health status/HRQoL (items 29 and 30 of the EORTC QLQ-C30.) Visit summary and change from baseline analyses will be performed for the EORTC QLQ-C30 GHS/HRQoL scale scores. Summary statistics (number of patients, mean, SD, median, minimum, maximum) of score(s) will be presented by treatment arm and longitudinal score change(s) from baseline to each time point while patients are receiving treatment will inform statistical differences between treatment arm (see section [4.4.3.2.4](#)).

4.4.3 Exploratory Efficacy Endpoints

4.4.3.1 ORR, DOR, and PFS by Investigator Using Immune-Modified RECIST

Objective response, DOR, and PFS according to immune-modified RECIST will be analyzed using the methods as described above.

4.4.3.2 Patient-Reported Outcomes

4.4.3.2.1 Analyses of Study Conduct

On the ITT population, completion analysis will be performed for the overall EORTC QLQ-C30 questionnaire. Completion rates will be summarized by number and proportion of patients among those expected to complete the QLQ-C30 at each time point. Reasons for non-completion will be summarized if available.

4.4.3.2.2 Visit Score Summary and Change from Baseline

PRO-evaluable population will include all randomized patients who have a baseline and at least 1 post-baseline assessment. On the PRO-evaluable population, visit summary and change from baseline analyses will be performed for the EORTC QLQ-C30 scales. Summary statistics (number of patients, mean, SD, median, minimum, maximum) of score(s) and score change(s) will be presented by treatment arm from baseline to each time point including time of disease progression per RECIST v1.1, time of clinical progression, at treatment discontinuation due to adverse event, and post-study treatment follow-up.

4.4.3.2.3 Proportion of patients

On the PRO-evaluable population, the number and proportion of patients with a clinically meaningful change of 10-points or greater will be summarized by treatment arm, for the EORTC QLQ-C30 scores at the same timepoints listed in Section 4.4.3.2.2. The 95% CI around the proportion will be calculated using the Clopper-Pearson method for each treatment arm. The difference in the proportions between the two treatment arms will be presented with a two-sided 95% CI based on a normal approximation to the binomial distribution.

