4.5.11 Patient-Reported Outcomes

To more fully characterize disease burden and clinical benefit of atezolizumab and cobimetinib in patients with advanced melanoma, patient-reported outcome (PRO) data will be obtained through use of the following instruments: EORTC QLQ-C30 and the EQ-5D-5L. The questionnaires will be translated as appropriate into the local language. Reminders will be provided in order to maximize compliance. It is critical to rigorously collect the PRO data as they support the secondary and exploratory efficacy endpoints.

The EORTC QLQ-C30 and EQ-5D-5L will be completed on Day 1 of Cycle 1 and every 4 weeks thereafter, including prior to tumor assessments visits every 8 weeks. In addition, the questionnaires will be completed at the site for the treatment discontinuation visit and at unscheduled visits. All PRO questionnaires must be completed prior to any study assessment(s) that could bias a patient's responses.

Also, the PROs will be collected every 4 weeks for 6 months after the treatment discontinuation visit. PRO data collected post-study treatment will be used as a unique opportunity to quantify patients' post-treatment experience in terms of humanistic outcomes.

Patients will use an electronic device to capture all PRO data. Instructions to use the device and to complete the PRO questionnaires will be provided by site staff once the patient is randomized and before initiation of study treatment. The data will be transmitted to a centralized database maintained by the vendor and will be made available for access by appropriate study personnel at the site. In the event that the device or the Web-based system is not readily available, paper questionnaires formatted for use as backup data collection forms should be used to minimize missing data. Compliance with data collection will be documented throughout the study.

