---------	---	----

LIST OF FIGURES

Figure 1	Study Schema.....	8
----------	-------------------	---

LIST OF APPENDICES

Appendix 1	Protocol Synopsis	24
Appendix 2	Schedule of Assessments.....	37
Appendix 3	Schedule of Pharmacokinetic, Immunogenicity, and Biomarker Samples.....	48
Appendix 4	Response Evaluation Criteria in Solid Tumors, Version 1.1.....	49

1. **BACKGROUND**

This Statistical Analysis Plan (SAP) provides details of the planned analyses and statistical methods for Study CO39722 (IMspire170): A Phase III, open-label, multicenter, two-arm, randomized study to investigate the efficacy and safety of cobimetinib plus atezolizumab versus pembrolizumab in patients with previously untreated advanced *BRAF*^{V600} wild-type melanoma. The background for the study can be found in the study protocol.

It is anticipated that positive results from Study CO39722 will support the submission of filing applications globally for the use of cobimetinib plus atezolizumab for the treatment of patients with previously untreated advanced *BRAF*^{V600} wild-type melanoma. For purposes of registration, the analyses outlined in this SAP will supersede those specified in the protocol.

2. **STUDY DESIGN**

[figure not shown]
Study CO39722 is a Phase III, multicenter, open-label, randomized study designed to evaluate the efficacy, safety, and pharmacokinetics of cobimetinib plus atezolizumab compared with pembrolizumab in treatment-naive patients with advanced *BRAF*^{V600} wild-type melanoma.

This study will be conducted globally and approximately 450 patients will be randomized in a 1:1 ratio to one of two treatment arms:

- Arm A: Patients will receive 60 mg of cobimetinib by mouth (PO) on a 21 days on, 7 days off (21/7) schedule (dosing on Days 1-21, followed by no dosing on Days 22-28) plus 840 mg of atezolizumab by intravenous (IV) infusion on Days 1 and 15 of each 28-day cycle (n=225).
- Arm B: Patients will receive 200 mg of pembrolizumab administered by IV infusion every 3 weeks (Q3W) (n=225).

The study schema is presented in [Figure 1](#).

Figure 1 Study Schema

PD=progressive disease; PD-L1=programmed death–ligand 1; Q3W=every 3 weeks; Q2W=every 2 weeks, R=randomization; RECIST v1.1=Response Evaluation Criteria in Solid Tumors, Version 1.1; 21/7=21 days on/7 days off (schedule).

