4.4.3.2.4 Mixed-Effect Model Repeated Measures Analysis

On the PRO-evaluable population, mixed-effects model repeated measures (MMRM) will be used for comparing the EORTC QLQ-C30 Role Functioning (RF), Physical Functioning (PF), and GHS/HRQoL scores between treatment arms. The model may include a term for intercept, a term for linear time trend, a term for treatment group, and a term for treatment-by-time interaction. Repeated measures over time may be accounted for by covariance structure. Time points with less than 20% patients who completed the RF, the PF, or the GHS/HRQoL scales, where all subsequent time points also have less than 20% completion will be excluded.

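### SAP 4.4.3.2.3 gives the between-arm difference in 10-point changers a normal-approximation 95% CI with no small-sample rule; read as an uncorrected Wald interval, it under-covers at sparse timepoints (minor, exploratory)

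*SAP*

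**What the plan says.** SAP 4.4.3.2.3 summarizes, by arm, the proportion of patients whose score changed by at least 10 points. Within arms the method is exact: "The 95% CI around the proportion will be calculated using the Clopper-Pearson method for each treatment arm". The difference between arms, however, "will be presented with a two-sided 95% CI based on a normal approximation to the binomial distribution". No variance form, continuity correction, minimum count or fallback is given.

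The summary is made "for the EORTC QLQ-C30 scores at the same timepoints listed in Section 4.4.3.2.2". Besides the scheduled visits, that section lists event-defined timepoints, including "time of clinical progression, at treatment discontinuation due to adverse event, and post-study treatment follow-up". Under Protocol 4.5.11 the questionnaires "will be completed on Day 1 of Cycle 1 and every 4 weeks thereafter".

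The population does not limit sparse timepoints: "PRO-evaluable population will include all randomized patients who have a baseline and at least 1 post-baseline assessment". The only cut-off for thin data, "Time points with less than 20% patients who completed the RF, the PF, or the GHS/HRQoL scales", is in SAP 4.4.3.2.4 and governs the mixed model alone.

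For the ORR difference, SAP 4.4.2.2 names a specific interval, Hauck-Anderson.

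**The concern.** The usual reading of a normal-approximation interval for a difference is the unpooled Wald interval. It performs poorly when one group is very small. Four-weekly visits with no cut-off, plus subsets defined by clinical progression or discontinuation due to an adverse event, make small groups likely.

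At those timepoints a table would show a sound exact interval for each arm beside a nominal 95% interval for the contrast that covers less than 95%. The adverse-event discontinuation timepoint is also one where readers look for tolerability signals. What is at stake is the reading of exploratory PRO tables, not a trial conclusion.

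**Working it through.** **Figure to reproduce.** Section 4.4.3.2.3 gives none beyond the nominal 95%. The PFS inputs borrowed below do reproduce SAP 2.3: √240/2 × |ln 0.55| − 2.576 = 2.055, i.e. 98.0% power (stated 98%), and exp(−2 × 2.576/√240) = 0.717 (stated 0.72).

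**Inputs from the documents.** "approximately 450 patients will be randomized in a 1:1 ratio to one of two treatment arms" (SAP 2), so 225 per arm. From SAP 2.3: median PFS 10.0 and 5.5 months, enrollment 12 months, dropout 5% per year, PFS analysis 17 months after first patient in.

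**Inputs assumed.** Exponential PFS stands in for time on the PRO schedule, enrollment is uniform, and every remaining patient returns a form. Changer rates and adverse-event discontinuation counts are not in the documents, so ranges are shown.

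**Patients left at month t (t ≥ 5) at the 17-month cutoff:** 225 × (17 − t)/12 × 0.5^(t/median) × 0.95^(t/12), Arm A then Arm B.

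- Month 6: 206.25 × 0.660 × 0.975 = 133; 206.25 × 0.469 × 0.975 = 94.
- Month 12: 93.75 × 0.435 × 0.950 = 39; 93.75 × 0.220 × 0.950 = 20.
- Month 14: 56.25 × 0.379 × 0.942 = 20; 56.25 × 0.171 × 0.942 = 9.
- Month 15: 37.5 × 0.354 × 0.938 = 12; 37.5 × 0.151 × 0.938 = 5.

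**Interval and coverage.** Wald: d ± 1.96 × √(p₁(1−p₁)/n₁ + p₂(1−p₂)/n₂), with observed proportions. Coverage is the sum, over all pairs (x₁, x₂), of the binomial probabilities of pairs whose interval contains the true difference.

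Wald / Newcombe coverage (%) for equal true rates:

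| n (A vs B) | 10% | 15% | 20% | 25% | 30% | 40% |
|---|---|---|---|---|---|---|
| 133 vs 94 (month 6) | 94.8 / 94.7 | 94.7 / 95.0 | 94.8 / 95.1 | 94.7 / 95.0 | 94.7 / 95.0 | 94.7 / 95.0 |
| 39 vs 20 (month 12) | 91.9 / 97.1 | 93.1 / 96.1 | 93.4 / 95.4 | 93.5 / 95.0 | 93.5 / 94.7 | 93.3 / 94.7 |
| 20 vs 9 (month 14) | 93.9 / 97.6 | 90.5 / 96.1 | 90.2 / 95.2 | 91.3 / 94.9 | 92.3 / 94.8 | 92.8 / 94.9 |
| 12 vs 5 (month 15) | 92.9 / 97.3 | 87.0 / 96.5 | 83.5 / 96.0 | 82.7 / 95.4 | 83.7 / 94.8 | 86.5 / 93.9 |
| 22 vs 7 (assumed AE discontinuations, 10% vs 3%) | 90.8 / 97.1 | 84.8 / 96.3 | 84.0 / 95.6 | 86.2 / 95.1 | 88.6 / 94.7 | 90.0 / 94.7 |
| 10 vs 10 | 95.0 / 99.1 | 92.2 / 97.9 | 90.9 / 97.0 | 90.6 / 96.5 | 90.5 / 96.3 | 90.8 / 96.0 |

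**Unequal rates.** At 12 vs 5, Wald covers 80.4% for 10% vs 30% and 86.4% for 20% vs 40%. Over all rate pairs from 10% to 50%, its median is 87.2%, and 89% of pairs fall below 90%; Newcombe's minimum is 93.4%.

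**Other assumed AE-discontinuation shares.** Over the same rate pairs, 15% vs 5% (34 vs 11 patients) gives a median Wald coverage of 91.6%, and 20% vs 10% (45 vs 22) gives 93.5%.

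**Over-coverage and the zero case.** At 10 vs 10 with both rates 5%, Wald covers 98.6%. Part of this is an artifact: with no changer in either arm the interval is [0, 0], which counts as covering a true difference of zero. At 10 vs 10 and 5% this happens with probability 0.95^20 = 36%; at 12 vs 5 and 10%, with probability 0.9^17 = 17%. For 0/8 vs 0/10, Newcombe gives about −0.28 to 0.32.

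**The case against.** **The variant is not named.** The SAP does not exclude a continuity correction, and a standard one mostly restores coverage: at 12 vs 5 it gives 95.8–99.7% for equal rates of 10–40%. This stands as a limit on the claim. The correction is not reliable with unequal arms and rates, however: 15 vs 5 patients with 10% vs 30% gives 81.4%. An unnamed variant is also a gap in itself.

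**Counts and rates are inferred.** The documents give neither. Insomnia is a single four-option item scored 0–100, so one category step is about 33 points and already passes the threshold; rates need not be low. That weakens any case built on low rates, but at 12 vs 5 coverage is still 86.5% at 40%. Treatment beyond progression would raise the counts and unreturned forms would lower them. SAP 2.5 records that no benefit was shown. If PFS was similar in the two arms, late-visit imbalance is smaller than projected.

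**Stronger readings that a reader might infer.**

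- *That visits at months 18 and 24 show severe under-coverage.* Ignoring the cutoff, 225 × 0.5^(24/10) = 43 and 225 × 0.5^(24/5.5) = 11, where Wald covers 79.5% at a 10% rate. At the planned 17-month cutoff nobody has reached those visits, and after early termination SAP 2.5 names only a final OS analysis.
- *That the interval is always too narrow.* It is not: it can over-cover with small equal arms at low equal rates, and it covers about 92–95% at 40 vs 20.
- *That this is the only between-arm comparison for insomnia, pain and fatigue.* That holds in the SAP, whose mixed model covers Role Functioning, Physical Functioning and GHS/HRQoL. Protocol 6.4.3 plans a longitudinal model not limited to those scales, and the SAP supersedes it only for filing.

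**The stakes are low.** No test uses these intervals. Subsets defined by progression or adverse-event discontinuation arise after randomization, so the arms are not comparable there under any interval.

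**Conclusion.** The point holds as a minor correction. The plan prescribes an asymptotic interval at timepoints where its own assumptions can leave about five patients in one arm, with no rule to stop or adapt it. Read as uncorrected Wald, coverage falls to about 83–87% at 12 vs 5 and about 84–90% at an assumed 22 vs 7, for equal rates of 15–40%. The shortfall is small by month 12 and negligible at early visits.

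These figures rest on the Wald reading, on planning-stage PFS as a proxy for form counts, and on assumed changer rates and AE-discontinuation shares. The documents do not support a claim that many intervals will falsely exclude zero. They support only that, at sparse timepoints, more than the nominal 5% may do so. The primary and key secondary conclusions are unaffected.

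**What to change.** In SAP 4.4.3.2.3, replace the reference to a normal approximation with a statement that the interval for the difference is calculated by the Newcombe (Wilson score) method or the Miettinen-Nurminen method, at all timepoints. Name one; Newcombe is the one checked above. Reusing Hauck-Anderson from the ORR analysis would improve on Wald, but it can still fall to about 85–87% at five per arm with unequal rates.

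The cost is one phrase and one program option. Intervals become wider at sparse timepoints where few patients change, and barely move at well-filled visits. If these tables have already been produced, the score interval can be shown beside the existing one and labeled as added.

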4.4.3.2.4 Mixed-Effect Model Repeated Measures Analysis

On the PRO-evaluable population, mixed-effects model repeated measures (MMRM) will be used for comparing the EORTC QLQ-C30 Role Functioning (RF), Physical Functioning (PF), and GHS/HRQoL scores between treatment arms. The model may include a term for intercept, a term for linear time trend, a term for treatment group, and a term for treatment-by-time interaction. Repeated measures over time may be accounted for by covariance structure. Time points with less than 20% patients who completed the RF, the PF, or the GHS/HRQoL scales, where all subsequent time points also have less than 20% completion will be excluded.

4.4.4 Exploratory Health Status Utility Endpoint

The EQ-5D-5L will be scored according to its manual, and results will be reported separately from the Clinical Study Report.

4.4.5 Sensitivity Analyses

The impact of missed scheduled tumor assessments on IRC-assessed PFS will be assessed depending on the number of patients who missed assessments. If > 5% of patients missed two or more assessments scheduled immediately prior to the date of disease progression per RECIST v1.1 or death, a sensitivity analysis will be performed where patients who missed two or more scheduled assessments immediately prior to the date of disease progression per RECIST v1.1 or death will be censored at the last tumor assessment prior to the missed visits.

A sensitivity analysis will also be conducted on IRC-assessed PFS to determine the impact of non-protocol anti-cancer therapy. Patients who die or progress after having received non-protocol anti-cancer therapy will be censored at the date of the last evaluable tumor assessment prior to start of non-protocol anti-cancer therapy.

If more than 5% of patients have central results that indicate their tumors are BRAF mutation positive, then a sensitivity analysis will be conducted on IRC-assessed PFS with these patients excluded.

Statistical methodologies analogous to those used in the analysis of PFS as specified in Section 4.4.1 will be used for these sensitivity analyses.

4.4.6 Subgroup Analyses

The consistency of the IRC-assessed PFS and OS results will be examined in subgroups defined by demographic and baseline characteristics and stratification factors. Summaries of PFS and OS, including the unstratified HR estimated from a Cox proportional hazards model and Kaplan-Meier estimates of median PFS and OS, will be produced separately for each level of the subgroup for the comparisons between two treatment arms and displayed in a Forest plot (Lewis and Clarke 2001).

Kaplan-Meier plots of OS and PFS will also be produced for selected subgroups.

Summaries of IRC-assessed ORR by subgroup will also be provided.

The subgroups to be considered include, but are not limited to, the following:

- Age (≤ 65 years, > 65 years) at randomization
- Race (non-White, White)
- Sex (female, male)
- PD-L1 status (IC0 vs. IC1, 2, 3)
- Baseline LDH (less than or equal to the ULN, greater than the ULN)

- Region (North America, Europe, Australia, New Zealand, others)
- ECOG performance status at randomization (0, 1)
- Disease Status (Locally advanced unresectable, metastatic)

4.5 SAFETY ANALYSES

Unless specified otherwise, the safety analyses described below will be conducted for the safety population with patients grouped according to study treatment received. Specifically, the treatment arms for safety analyses will be defined as follows:

- Cobimetinib+atezolizumab arm (Arm A): patients who received any amount of cobimetinib or atezolizumab
- Pembrolizumab arm (Arm B): patients who received any amount of pembrolizumab without any amount of either atezolizumab or cobimetinib.

If a patient did not receive any amount of cobimetinib, atezolizumab, or pembrolizumab, the patient will not be included in the safety analyses.

4.5.1 Exposure of Study Medication

Study drug exposure, including treatment duration, number of cycles, and dose intensity, will be summarized for each treatment arm with descriptive statistics.

4.5.2 Adverse Events

Verbatim description of AEs will be summarized by mapped terms and appropriate thesaurus levels and graded according to NCI CTCAE v4.0. All AEs that occur during or after the first study drug dose will be summarized by treatment arm and NCI CTCAE grade. In addition, serious adverse events (SAEs), severe AEs (Grade ≥ 3), adverse events of special interest (AESI), and AEs leading to study drug discontinuation or interruption will be summarized accordingly. Multiple occurrences of the same event will be counted once at the maximum severity. The proportion of patients who experience at least one AE event will be reported by toxicity term and treatment arm.

All deaths and causes of death will be summarized by treatment arm.

Listings of AEs will include all AEs with an onset that occurred on or after the first study drug treatment up to the data cutoff date.

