4.5.9 Left Ventricular Ejection Fraction

All patients will require evaluation of LVEF at screening, and only patients receiving cobimetinib (Arm A) will require subsequent evaluations of LVEF.

Evaluation of LVEF by ECHO or MUGA must be performed at the following timepoints:

- Screening
- Day 1 of Cycle 2 (± 1 week)
- Day 1 of every three treatment cycles and starting at Cycle 5 and thereafter (± 2 weeks)
- The treatment discontinuation visit evaluation of LVEF does not need to be performed at the treatment discontinuation visit if an evaluation has been performed within the last 12 weeks and there are no clinically significant findings and/or changes from baseline.
- All patients restarting treatment with a dose reduction of cobimetinib because of a decrease in LVEF should have LVEF measurements taken after approximately 2 weeks, 4 weeks, 10 weeks, and 16 weeks, and then resume monitoring of LVEF every three treatment cycles.

Any patient who develops clinical signs or symptoms suspicious of cardiac failure should undergo an LVEF assessment. Evaluation of LVEF must be performed using the same method (ECHO or MUGA) for each patient. It is strongly encouraged that the same laboratory and operator perform ECHO or MUGA scans for each individual patient. Investigators must be aware of local institution regulations regarding repeat MUGA scans. The repeat administration of radioisotopes is limited in some nuclear medicine laboratories, and some patients in this study could require monitoring on four or more occasions.

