4.5.10 Ophthalmologic Examination

All patients will require an ophthalmologic examination at screening, and only patients receiving cobimetinib (Arm A) will require subsequent ophthalmologic examinations.

Ophthalmologic examination must be performed at the following timepoints:

- Screening
- Day 1 of Cycle 2 (\pm 1 week)
- Day 1 of Cycles 5, 8, and 11 (every three treatment cycles; \pm 2 weeks)
- Day 1 of Cycles 15, 19, and 23 (every four treatment cycles; \pm 2 weeks)
- Day 1 of Cycles 29, 35, 41, 47, etc. (every six treatment cycles; \pm 2 weeks)
- Treatment discontinuation visit: The treatment discontinuation visit evaluation does not need to be performed if an evaluation has been performed within the last 12 weeks and there are no clinically significant findings and/or changes from baseline.

The objective of baseline ophthalmologic examination is to evaluate for evidence of retinal pathology that may be a risk factor for central serous retinopathy or RVO. Ophthalmologic examination must be performed by a qualified ophthalmologist. Risk factors for RVO include uncontrolled serum cholesterol, hypertriglyceridemia, hyperglycemia, hypertension, and glaucoma. See Sections 4.1.2.1 and 4.1.2.3.3 for inclusion and exclusion criteria.

Baseline and serial surveillance ophthalmologic examination will include visual acuity testing, intraocular pressure measurements by tonometry, slitlamp ophthalmoscopy, indirect ophthalmoscopy, and spectral-domain optical coherence tomography. Spectral-domain optical coherence tomography, if not available, may be substituted with time-domain optical coherence tomography.

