5.1.1.1.2 Serous Retinopathy

Serous retinopathy (fluid accumulation within the layers of the retina) has been observed in patients treated with MEK-inhibitors, including cobimetinib (Flaherty et al. 2012). Manifestations of serous retinopathy include visual disturbances, findings of retinal detachment, and retinopathy. Serous retinopathy events may also be asymptomatic.

Serous retinopathy has been characterized in Study GO28141. The study incorporated prospective serial ophthalmologic examinations for all enrolled patients. Serous retinopathy was reported more frequently in patients treated with cobimetinib plus vemurafenib than placebo plus vemurafenib (25.5% vs. 2.8%, respectively), and approximately half the events were asymptomatic Grade 1 events. Few patients treated with cobimetinib plus vemurafenib experienced Grade ≥ 3 ocular events (2.8%); the majority of these events were managed with dose modification of both cobimetinib and vemurafenib.

To address serous retinopathy with cobimetinib treatment, all patients are required to undergo a baseline ophthalmologic examination to assess for history or evidence of retinal pathology that is considered to be a risk factor for or indicative of neurosensory retinal detachment, central serous chorioretinopathy, neovascular retinopathy, or retinopathy of prematurity. Patients will also undergo ophthalmologic examinations at specified timepoints throughout the study (see [Appendix 1](#)). Details regarding baseline and subsequent ophthalmologic examinations are provided in Section [4.5.10](#).

Guidelines for management of patients who develop Grade ≥ 2 visual disorders or retinopathy are provided in [Appendix 10](#).

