5.1.1.1.3 Left Ventricular Dysfunction

Decreases in LVEF from baseline have been reported in patients receiving cobimetinib. Left ventricular dysfunction may occur with signs and symptoms of cardiac failure, or reduction in LVEF events may be asymptomatic.

Left ventricular dysfunction has been characterized in Study GO28141. The study incorporated prospective serial LVEF evaluations in all patients. With active surveillance, measured Grade 2 or 3 reductions in LVEF were observed more frequently in patients treated with cobimetinib plus vemurafenib than placebo plus vemurafenib (8.5% vs. 3.7%, respectively). Of the patients treated with cobimetinib plus vemurafenib, 2 patients (0.8%) had symptomatic reduction in LVEF and the remaining patients were asymptomatic. Most LVEF reduction events in patients treated with cobimetinib plus vemurafenib (62%) improved or resolved with management according to dose modification guidelines (see [Appendix 10](#)).

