5.2.3 Adverse Events of Special Interest (Immediately Reportable to the Sponsor)

Adverse events of special interest are required to be reported by the investigator to the Sponsor immediately (i.e., no more than 24 hours after learning of the event; see Section 5.4.2 for reporting instructions). Adverse events of special interest for this study are as follows:

- Cases of potential drug-induced liver injury that include an elevated ALT or AST in combination with either an elevated bilirubin or clinical jaundice, as defined by Hy's Law (see Section 5.3.5.7) and based on the following observations:
 - Treatment-emergent ALT or AST $> 3 \times$ baseline value in combination with total bilirubin $> 2 \times$ ULN (of which $\geq 35\%$ is direct bilirubin)
 - Treatment-emergent ALT or AST $> 3 \times$ baseline value in combination with clinical jaundice
 - Hepatitis, including AST or ALT $> 10 \times$ ULN
 - Significant liver toxicity
- Suspected transmission of an infectious agent by the study treatment, as defined below
 - Any organism, virus, or infectious particle (e.g., prion protein transmitting transmissible spongiform encephalopathy), pathogenic or non-pathogenic, is considered an infectious agent. A transmission of an infectious agent may be suspected from clinical symptoms or laboratory findings that indicate an infection in a patient exposed to a medicinal product. This term applies only when a contamination of study treatment is suspected.
- Pneumonitis
- Colitis
- Endocrinopathies: diabetes mellitus, pancreatitis, adrenal insufficiency, hyperthyroidism, and hypophysitis
- Systemic lupus erythematosus

- Neurological disorders: Guillain-Barré syndrome, myasthenic syndrome or myasthenia gravis, and meningoencephalitis
- Events suggestive of hypersensitivity, IRRs, cytokine-release syndrome (CRS), influenza-like illness, HLH, and MAS
- Nephritis
- Ocular toxicities
 - Uveitis or retinitis
 - RVO
 - Serous retinopathy, including events of retinal detachment, retinal pigment epithelium detachment, neurosensory retinal detachment, and central serous chorioretinopathy
- Myositis
- Cardiac disorders for the following events
 - Grade ≥ 2 cardiac disorders, including atrial fibrillation, myocarditis, and pericarditis
 - Symptomatic heart failure or Grade ≥ 3 reduction in LVEF
- Vasculitis
- Myopathies, including rhabdomyolysis or Grade ≥ 3 CPK elevation
- Grade ≥ 3 hemorrhage or any-grade cerebral hemorrhage
- Grade ≥ 3 rash
- Grade ≥ 3 diarrhea

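### After screening, LVEF and eye examinations are scheduled only in Arm A, but SAP 4.5.2 sets the resulting adverse events side by side by arm with no allowance for unequal ascertainment

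*SAP*

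**What the plan says.** **Schedule.** All patients have an LVEF measurement and an eye examination at screening. After that, under protocol 4.5.9, "only patients receiving cobimetinib (Arm A) will require subsequent evaluations of LVEF", and under 4.5.10, "only patients receiving cobimetinib (Arm A) will require subsequent ophthalmologic examinations". The schedules of activities (protocol Appendix 1, repeated in SAP Appendix 2) agree: the pembrolizumab table marks both examinations at screening only. Outside the schedule, 4.5.9 adds a trigger that applies in either arm: "Any patient who develops clinical signs or symptoms suspicious of cardiac failure should undergo an LVEF assessment". Protocol 4.5.3 also has Arm A patients, and only them, asked about vision at each physical examination.

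**What is counted.** Protocol 5.2.3 lists serous retinopathy as an AESI with no grade threshold, and also "Symptomatic heart failure or Grade ≥ 3 reduction in LVEF". Under 5.2.1, a deterioration in a clinical test that changes study treatment is an adverse event. Appendix 10, Table 6 links certain asymptomatic LVEF falls to interruption of cobimetinib.

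**Analysis.** SAP 4.5.2 reports all AEs by arm and grade, and the proportion of patients with each term by arm. Grade ≥3 AEs are treated in the same way, and "adverse events of special interest (AESI), and AEs leading to study drug discontinuation or interruption will be summarized accordingly". Neither SAP 4.5 nor protocol 6.5 mentions mode of detection, numbers examined or the different schedules. The safety objective (protocol Section 2, Table 1) is comparative.

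**The concern.** A silent fall in LVEF or a silent retinal finding becomes an adverse event only if someone looks. In Arm A someone looks on a schedule. In Arm B, after screening, an LVEF measurement needs a clinical reason and no eye examination is scheduled. The protocol itself calls most of these events asymptomatic or mild (3.3.8). An Arm A echocardiogram can generate an AE, and an AE leading to interruption, for which a similar silent change in Arm B leaves no record.

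A reader who subtracts the two columns, as a comparative objective invites, would attribute the whole gap to the drugs. Protocol 4.5.5 keeps the tumor assessment schedule the same in both arms for this very reason. For the safety examinations, 3.3.8 justifies the asymmetry by the burden on control patients. That is a fair reason for the schedule, but it leaves the analysis question open.

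**Working it through.** The plan states no figure on this point, so there is none to reproduce. The illustration uses the protocol's summary of Study GO28141 (cobimetinib plus vemurafenib against placebo plus vemurafenib), in which all patients in both arms had serial LVEF and eye examinations.

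**Inputs**
- LVEF, protocol 5.1.1.1.3: "With active surveillance, measured Grade 2 or 3 reductions in LVEF were observed more frequently", at 8.5% against 3.7%. Of the cobimetinib patients, 2 (0.8%) had a symptomatic reduction.
- Serous retinopathy, protocol 5.1.1.1.2: 25.5% against 2.8%, and "approximately half the events were asymptomatic Grade 1 events".
- Planned arm size: 225.

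**Formula.** Let a be the rate in the examined arm, c the true control rate, and f the share of control events found without scheduled examination. The true difference is a − c. The apparent difference is a − c·f, so the inflation is c·(1 − f). The value of f is unknown. The range 0 to 0.5 is shown, with f = 1 as the equal-examination reference.

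| f | LVEF: control seen | LVEF: difference (points) | LVEF: ratio | Retinopathy: control seen | Retinopathy: difference (points) | Retinopathy: ratio |
|---|---|---|---|---|---|---|
| 1 | 3.7% | 4.8 | 2.3 | 2.8% | 22.7 | 9.1 |
| 0.5 | 1.85% | 6.65 | 4.6 | 1.4% | 24.1 | 18.2 |
| 0 | 0% | 8.5 | – | 0% | 25.5 | – |

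- LVEF inflation: 1.85 to 3.7 points, which is 1.85/4.8 = 39% to 3.7/4.8 = 77% of the true difference.
- Retinopathy inflation: 1.4 to 2.8 points, which is 1.4/22.7 = 6% to 2.8/22.7 = 12%.
- The symptomatic share among cobimetinib LVEF events is 0.8/8.5 = 0.094. If that share also described control detection, the LVEF difference would be 8.5 − 3.7 × 0.094 = 8.15 points, within the range above.
- Protocol 3.3.8 gives slightly different retinopathy rates (24% against 2.1%). They lead to the same picture: 21.9 points becomes 22.95 (f = 0.5) to 24.0 (f = 0).

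**No true LVEF effect.** With 3.7% in both arms of 225, Arm A would show 225 × 0.037 = 8.3 patients. Arm B would show 4.2 at f = 0.5 and 0.8 at f = 0.094. The apparent excess is 1.85 to 3.35 points, all of it from surveillance.

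**What cannot be computed.** The LVEF rates are for Grade 2 or 3 combined, whereas the LVEF-specific AESI starts at Grade 3. The protocol gives no Grade ≥3 LVEF rate by arm from GO28141, so the inflation of the Grade ≥3 and AESI totals has no documented size.

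**The case against.** Several points on the other side stand.

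- **The SAP is silent; it makes no false claim.** A reader might infer that the SAP treats both arms as equally examined, or that a biased test is planned. It does neither. It plans descriptive proportions, with no AE test or risk difference, and its own Appendix 2 shows both schedules.
- **Arm B is not at zero.** Symptoms trigger an LVEF assessment in either arm, so f = 0 is a limit and not an expectation.
- **The reference rates are borrowed.** The GO28141 control was placebo plus vemurafenib, not pembrolizumab, and the symptomatic share comes from two cobimetinib patients.
- **The ocular part is small on the difference scale.** About half the retinopathy events were silent and Grade 1. These cannot enter the Grade ≥3 totals, and Appendix 10, Table 5 continues dosing at Grade 1, so they should not feed the interruption totals either. They do count as AESIs.
- **Findings made by examination are real.** A Grade ≥3 LVEF fall, or an interruption after a silent fall, is toxicity or burden of the regimen as given. Taking these out of the main totals would hide it.
- **A symptomatic-only comparison is not clean.** Only Arm A is asked directly about vision, and interruption after a silent LVEF fall may prevent later symptoms in Arm A. No data field for mode of detection is described, and examination windows of one to two weeks around cycle visits blur linkage by date.
- **Timing.** SAP version 3 was written after the primary endpoint was missed, so any split is post hoc. No efficacy conclusion or decision rule depends on it.

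These points limit the size of the concern and shape the remedy. They do not remove the gap: nothing in the analysis text tells a reader that two of the AESI types were actively looked for in one arm only.

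**Conclusion.** The concern holds for events found by scheduled examination. Following SAP 4.5.2 as written gives by-arm proportions that overstate Arm A's excess of asymptomatic LVEF reduction, and to a lesser degree of asymptomatic serous retinopathy. If GO28141 rates apply and f lies between 0 and 0.5, the Grade 2–3 LVEF difference moves from 4.8 to between 6.65 and 8.5 points, and the retinopathy difference from 22.7 to between 24.1 and 25.5. The LVEF distortion is material. For retinopathy the difference barely moves, although the ratio at least doubles.

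Two stronger readings are not supported. One is that the Grade ≥3 and AESI totals are inflated by a known amount: the documents give no rate from which to size that. The other is that the safety comparison as a whole is unreliable. The problem is confined to these examination-dependent events; CPK, for example, is in the chemistry panel of both arms. Efficacy is unaffected.

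**What to change.** Keep the tables and totals planned in SAP 4.5.2 and add:

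1. A footnote to the AE, AESI and interruption tables saying that LVEF and eye examinations after screening were scheduled only in Arm A, with the number of patients per arm who had at least one post-baseline LVEF measurement and at least one post-baseline eye examination.
2. A supplementary table splitting LVEF-decrease and ocular AEs into symptomatic events and asymptomatic examination findings. Classify by recorded symptoms, grade and AE term, and by examination date where available. Limit between-arm statements to the symptomatic category, noting that only Arm A was asked specifically about vision. Describe asymptomatic findings for Arm A alone.
3. A sensitivity repeat of the AESI, Grade ≥3 and interruption totals without asymptomatic examination-only findings, shown beside the main totals and not in place of them.

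The cost is some SAP wording, a few tables and a derivation rule. Some events will be unclassifiable and should be reported as such, and the additions should be labelled post hoc. SAP 2.5 still refers to a final database lock to come, so the safety output can be adapted. No change to monitoring or treatment is involved.
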